**2) Author of Protocol**

- UC Davis Researcher
- Researcher from other institution
- Private Sponsor
- Cooperative Group
- Other: UCD Resident

**3) IRB Review History**

None

**4) Objectives**

The purpose of this study is to analyze the effect of subthreshold micropulse diode laser in the treatment of central-involving diabetic macular edema in eyes with good visual acuity defined as 20/32 or better on ETDRS testing, compared to observation alone (sham treatment).

We hypothesize that eyes treated with subthreshold micropulse diode laser will demonstrate either a significant improvement or stabilization of visual acuity at 12 and 24 months, or a significant delay in vision loss to 20/40 or worse, requiring initiation of anti-vascular endothelial growth factor (anti-VEGF) therapy.

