**7) Study Timelines**

- The duration of an individual subject’s participation in the study will be two years which will include at least 10 total visits at various time points including on the day of enrollment, followed by 1, 3, 6, 9, and 12, 15, 18, 21, 24 months after the day of enrollment
- The duration anticipated to enroll all study subjects is 1 year
- The estimated date for the investigators to complete this study is December 2023
- 36 eyes will be enrolled based on power calculations for 80% power assuming at least 40% of eyes monitored by observation alone will experience vision loss to 20/40 or worse, and that SML treatment will reduce that value to 15%, using a 2:1 ratio for randomization (2 treatment : 1 observation (sham)). The ETDRS study showed that among eyes with good visual acuity (20/25 or better), 40% will experience a visual acuity decrease by 5 letters or more. We assume a higher rate among eyes with 20/32 or better.

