**8) Study Endpoints**

Primary outcome:

- Proportion of patients with vision loss to 20/40 or worse on ETDRS testing on two visits  $\leq 28$  days apart at 12 and 24 months.
- Mean time to vision loss to 20/40 or worse on ETDRS testing on two visits  $\leq 28$  days apart

Secondary Outcomes:

- Mean change in visual acuity, low luminance visual acuity and contrast sensitivity at 3, 6, 9, 12, 15, 18, 21, and 24 months from baseline
- Mean change in central macular thickness (CMT) on OCT at 3, 6, 9, 12, 15, 18, 21, and 24 months from baseline
- Mean change in retinal sensitivity assessed by microperimetry at 3, 6, 9, 12, 15, 18, 21, and 24 months from baseline
- Percentage of subjects with visual acuity loss (including low luminance visual acuity and contrast sensitivity) of  $\geq 5$  letters at 12 and 24 months
- Percentage of subjects with at least 10 and 15 letter gain or loss at 12 and 24 months
- Visual acuity area under the curve at 12 and 24 months
- Number of SML treatments received at 12 and 24 months
- Number of anti-VEGF treatments received at 12 and 24 months
- *Any safety concerns documented during the study*

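### The hypothesis, the primary outcomes and the sample size do not name one common test, which leaves open which result would count as success

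*Protocol*

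**What the plan says.** Four places in the protocol bear on what the trial is meant to show.

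- **Section 4, Objectives.** The hypothesis is disjunctive: "either a significant improvement or stabilization of visual acuity at 12 and 24 months, or a significant delay in vision loss" to 20/40 or worse. The stated comparator is sham. No margin or definition is given for stabilization.
- **Section 5, Background, closing paragraph.** The hypothesis is conjunctive: the laser is expected to improve acuity, anatomy and retinal sensitivity, and also to prevent vision loss by postponing anti-VEGF treatment.
- **Section 8, Study Endpoints.** There are two primary outcomes and no order between them. The first is "Proportion of patients with vision loss to 20/40 or worse on ETDRS testing on two visits" that are "days apart at 12 and 24 months". The second is "Mean time to vision loss to 20/40 or worse on ETDRS testing on two visits" under the same confirmation rule. Acuity change, the first limb of the section 4 hypothesis, is secondary: "Mean change in visual acuity, low luminance visual acuity and contrast sensitivity at 3, 6, 9, 12, 15, 18, 21, and 24 months from baseline".
- **Section 7, Study Timelines.** The sizing reads "36 eyes will be enrolled based on power calculations for 80% power assuming at least 40% of eyes monitored by observation alone" will lose vision to 20/40 or worse, against 15% with laser, randomized 2:1. No month is given for either rate. The supporting historical figure is for a loss of 5 letters or more, which is a different event.

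The protocol states no significance level and no sidedness.

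**The concern.** A reader cannot tell from the protocol which single comparison decides the trial. The section 4 wording allows success by more than one route, section 5 asks for everything at once, section 8 offers three readouts of equal rank, and section 7 is sized for one readout without a date. With about 24 laser and 12 sham eyes, chance differences between readouts will be large. A positive report could rest on whichever month or form of the outcome crosses the threshold, and that would be weak evidence that the laser prevents vision loss.

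Two of the terms also cannot be analysed as written. Stabilization without a margin cannot be shown or refuted. Mean time to loss is undefined for eyes that never lose vision, and under the plan's own rates those are most of the eyes.

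**Working it through.** **1. The plan's own figure.** Inputs from section 7: p1 = 0.40 (sham), p2 = 0.15 (laser), r = 2 laser eyes per sham eye, 80% power. Assumption: two-sided 5%.

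Pooled proportion = (0.40 + 2 × 0.15)/3 = 0.2333.

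Sham eyes = [1.96 × √(1.5 × 0.2333 × 0.7667) + 0.8416 × √(0.40 × 0.60 + 0.15 × 0.85/2)]² / 0.25² = (1.0153 + 0.4638)² / 0.0625 = 35.005.

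Rounded up, this is 36 sham and 72 laser eyes, 108 in total. Other standard variants (one-sided, continuity-corrected, arcsine, unpooled) give totals of 84 to 123. None gives 36 in total.

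Power with 12 sham and 24 laser eyes = Φ[(0.25 × √12 − 1.0153)/0.5511] = Φ(−0.27) = 39%. Exact calculation gives 42% with chi-square and 30% with Fisher. One-sided 5% gives 51%.

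**2. Mean time to loss.** Expected events = 12 × 0.40 + 24 × 0.15 = 8.4 of 36 eyes if the rates are 24-month rates. The other 27.6 eyes have no time to average.

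**3. Chance of a false positive over the primary readouts.** Assumptions: no true difference, 24:12 independent eyes, no dropout, exponential event times read at the scheduled visits, each test at two-sided 5%, no adjustment, and any one positive test counting as success. The readouts are the 12-month proportion, the 24-month proportion and the log-rank test. Results from 3,000 trials per row:

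| 24-month loss | chi-square + log-rank | Fisher + log-rank |
|---|---|---|
| 20% | 7.0% | 4.5% |
| 40% | 7.7% | 6.5% |
| 60% | 10.0% | 6.4% |

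The simulation error is about √(0.08 × 0.92/3000) = 0.5 percentage points. Repeat runs gave 7.6-9.9% and 5.7-7.4%. Rounded, that is about 8-10% and 6-7%, and somewhat less when events are few. Three independent tests would give 1 − 0.95³ = 14.3%, and the upper bound is 3 × 5% = 15%. The simulated values are lower because the readouts are versions of one event.

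Counting only significant results in favour of laser, the chance is 5.2-5.3% with chi-square or 3.8% with Fisher, against a nominal 2.5%.

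**4. Adding acuity change at 12 and 24 months.** With assumed correlations between acuity and the event, the chance of any positive result rises to about 12-17%. This requires outcomes that section 8 lists as secondary.

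**5. If both months are required.** The probability that two tests are both positive cannot exceed that of either one, so the pair then adds no inflation.

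**The case against.** The strongest reply is that section 4 states a scientific hypothesis, not a decision rule. It names no test, level or condition for declaring success, and section 5 words the hypothesis conjunctively. A ranking or multiplicity rule may stand in a statistical analysis plan that is not available here, and its absence from the protocol would then be no fault. This stands in part. A reader might infer that the protocol itself fixes an any-positive rule, but the two conflicting hypotheses show that it fixes no rule at all. What does not stand is leaving the choice of primary outcome to a later document. That choice belongs in the protocol, and sections 4, 5, 7 and 8 already make it in conflicting ways.

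A reader might also infer a false-positive rate near 15% in place of 5%. The documents do not support this. The 5% level is itself an assumption, the upper figure needs the secondary acuity outcomes, and with an exact test, a natural choice with 12 sham eyes, the excess is small or absent.

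A third tempting reading is that a non-significant decline within the laser arm would be called stabilization. With an assumed SD of 6 to 8 letters, a mean loss of 2.069 × SD/√24, or about 2.5 to 3.4 letters, would be non-significant in 24 eyes. But no such one-arm test is planned: section 4 sets the comparison against sham, and the word significant may govern stabilization as well. The figure shows only why a margin is needed.

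Finally, because 36 equals the sham-arm size in the formula above, a reader might infer that one arm was mistaken for the total. The protocol does not show how 36 was derived, so this remains a guess.

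**Conclusion.** The point holds as a mismatch between hypothesis, primary outcomes and sizing. If any primary readout counted, unadjusted at an assumed two-sided 5%, the false-positive chance would be about 8-10% (chi-square plus log-rank) or 6-7% (Fisher plus log-rank), on the assumptions listed above. That is a modest inflation. It would exceed this range only if the acuity limb of section 4 also counted, and if section 8 requires both months, the pair of proportions contributes none. Stabilization cannot serve as a success criterion without a margin, and mean time to loss cannot be computed for most eyes. Separately, whichever readout is chosen, 36 eyes at 24:12 do not give the stated 80% power for 40% against 15%. The figure is about 40%.

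**What to change.** - **Section 8:** name one primary outcome. One option is time to first confirmed loss to 20/40 or worse through 24 months, described by Kaplan-Meier curves and compared by log-rank, replacing mean time. Make the 12- and 24-month proportions supportive.
- **Sections 4 and 5:** state the same hypothesis in both places, on that outcome and against sham. Remove the either/or construction and the word stabilization.
- **Section 7:** say which outcome and month the 40% and 15% describe, state the significance level, and restate the power.

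The time-to-event choice does not remove the power problem. If the rates are 24-month rates, the hazard ratio is ln 0.85/ln 0.60 = 0.318. Events needed = (1.96 + 0.8416)² / [(1/3)(2/3)(ln 0.318)²] ≈ 27, against 8.4 expected, which gives power of about 35%. Keeping all three readouts as co-equal alternatives with a Bonferroni split would cost more: for one proportion at α = 0.0167, 141 eyes are needed, and 36 eyes give 25% power.

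The change to the outcomes and the hypothesis is wording only. The sponsor gives up alternative routes to a positive claim and must either enlarge the trial or report its power as it is.

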**5) Background**

Diabetic retinopathy is one of the most common complications of diabetes and diabetic macular edema (DME) is one of the most common causes of vision loss in diabetes. Various treatment strategies for diabetic macular edema include focal or grid laser, anti-vascular endothelial growth factor (anti-VEGF), and corticosteroid treatments. The Early Treatment of Diabetic Retinopathy Study (ETDRS) in the 1980s and 1990s, which included patients with moderate to severe non-proliferative diabetic retinopathy (NPDR) or mild proliferative diabetic retinopathy (PDR), revealed that focal photocoagulation is effective in reducing the risk of moderate vision loss from DME by 50%. Focal laser was also shown to be more effective with fewer side effects than intraocular steroids such as triamcinolone acetonide in the treatment of DME in eyes with visual acuity of 20/40 or worse, making focal laser a benchmark against which other treatments were compared. Results of the Diabetic Retinopathy Clinical Research network (DRCR.net) Protocol-I established a new benchmark and revealed that in eyes with DME and visual acuity of 20/32 or worse, intravitreal anti-VEGF therapy using ranibizumab with prompt or deferred focal laser was superior to focal laser alone. More recently, the RIDE and RISE studies revealed that in eyes with visual acuity of 20/40 or worse, patients treated with ranibizumab had 15 or more letters of visual acuity gain compared to sham injections. Current treatment guidelines for DME are largely derived from DRCR network Protocol T, which has addressed the relative efficacy of various anti-VEGF agents in improving visual acuity, and decreasing central foveal thickness. However, all major clinical trials in management of DME

## **PROTOCOL TITLE: Micropulse for suppression of diabetic macular edema “PULSE STUDY”**

have only addressed eyes with visual acuity of 20/32 or worse. To date, there are no consensus on the best treatment approach for center-involving DME with good visual acuity (20/25 or better). The DRCR.net Protocol V is an ongoing randomized controlled study to determine if prompt anti-VEGF therapy can preserve vision in eyes with DME and good visual acuity of 20/25 or better. While this study has not yet been completed, intravitreal anti-VEGF therapy is not without risk, some of which include endophthalmitis, elevated intraocular pressure, and systemic vascular events. We hypothesize that early management of DME with good visual acuity requires treatment with a less invasive strategy.

A recently-developed treatment for DME is subthreshold micropulse laser (SML). In contrast to focal laser, SML delivers laser energy in a “chopped” fashion allowing the tissue to cool between pulses to eliminate thermal injury to the retina. Previous studies have shown the superiority of SML to conventional focal/grid laser photocoagulation in improving visual acuity. In eyes undergoing anti-VEGF therapy for DME, SML may reduce the frequency of injections. Unlike traditional “focal” laser therapy which are associated with macular scarring and choroidal neovascularization, SML are not associated with any of these complications, even after multiple treatments. While some physicians employ SML for treatment of DME in eyes with good visual acuity, due to the safety of this laser, there are no clear evidence supporting their use. Hence, there remains no consensus for standard of care for whether observation, anti-VEGF injection, focal/grid laser, or SML should be used for eyes with visual acuity of 20/25 or better. As most patients with good visual acuity are reluctant to undergo an intraocular injection which has greater risks associated such as endophthalmitis, vitreous hemorrhage, or retinal detachment, we seek to assess the potential benefit of SML laser alone vs. observation (sham) in this selection of eyes in preserving vision and anatomy.

The ETDRS study employed biomicroscopy, fundus photography, and fluorescein angiography as the standard modalities for assessing the presence and extent of DME. Since that time, newer methods are available to characterize DME including optical coherence tomography (OCT), fundus autofluorescence (FAF), and OCT angiography (OCT-A). Similarly, while visual acuity testing has been the most common method for functional assessment, newer methods such as microperimetry are being utilized to evaluate and quantify functional outcome by means of retinal sensitivity. The evaluation of retinal sensitivity is done through visual field testing. However, traditional visual field tests are not sensitive enough to identify small scotomas, especially when fixation is altered by macular edema. Microperimetry is a visual field test that has a fundus tracking system allowing it to overcome fixation instability. Furthermore, the stimulus used to assess retinal sensitivity is projected in the identical retinal area during the initial and subsequent examinations, thereby allowing identification of small scotomas and eccentric fixation. This is critical in preserving fixation when treating the macular edema with photocoagulation

Microperimetry has gained recent popularity in assessing functional impairment in patients with DME, allowing a correlation between retinal morphology (macular thickness) and retinal sensitivity. For example, Verma et al have shown decreased retinal sensitivity correlating with decreased foveal thickness in individuals with diabetes without diabetic retinopathy. Others have shown improved retinal sensitivity in eyes with DME after SML treatment when assessed by microperimetry. These studies underscore the importance of microperimetry in quantifying visual function in eyes with DME, particularly in eyes with good visual acuity where an improvement in visual acuity may not be readily discernable.

## **PROTOCOL TITLE: Micropulse for suppression of diabetic macular edema “PULSE STUDY”**

Our goal in this study is to assess the effect of subthreshold micropulse diode laser in eyes with DME and good visual acuity defined by vision of 20/32 or better based on ETDRS testing. We hypothesize that subthreshold micropulse diode laser will significantly improve visual acuity, retinal anatomy, and retinal sensitivity on microperimetry, and also prevent vision loss by delaying the need for anti-VEGF therapy compared to observation alone.

### **6) Inclusion and Exclusion Criteria**

Subjects will be recruited from patients seen at the UC Davis Eye Center retina clinic who are willing and eligible to participate based on our inclusion criteria.

#### **Inclusion Criteria:**

1. Age  $\geq$ 18 years
2. Type 1 or type 2 diabetes mellitus
3. Clinical evidence of center-involved DME confirmed on OCT, and defined by OCT Central Subfield (CSF) thickness at the time of randomization by the following:
  - a. Zeiss Cirrus: 275 $\mu$  in women, and 290 $\mu$  in men
  - b. Heidelberg Spectralis: 290 $\mu$  in women, and 305 $\mu$  in men
4. Best corrected visual acuity of 20/32 or better on ETDRS testing

#### **Exclusion Criteria:**

1. Macular edema from causes other than DME
2. An ocular condition is present such that in the opinion of the investigator, visual acuity would not improve from resolution of macular edema (i.e/foveal atrophy, pigment abnormalities, dense hard exudates)
3. An ocular condition is present other than DME which may contribute to macular edema (i.e/vein occlusion, ERM, uveitis, RP, etc...).
4. Cataract that in the opinion of the investigator may alter visual acuity throughout the course of the study
5. History of prior laser or other surgical, intravitreal, or peribulbar treatment for DME in the study eye within the prior 6 months.
6. More than 4 prior intraocular injections for treatment of DME at any time
7. More than 1 prior focal/grid macular photocoagulation session for treatment of DME at any time
8. History of topical steroid or NSAID treatment within 30 days prior to randomization
9. History of PRP within 4 months prior to randomization or anticipated need for PRP in the 6 months following randomization.
10. Any history of vitrectomy.
11. History of major ocular surgery (cataract extraction, scleral buckle, any intraocular surgery, etc.) within prior 4 months or anticipated within the next 6 months following randomization
12. History of YAG capsulotomy performed within 2 months prior to randomization.
13. Aphakia
14. Exam evidence of external ocular infection, including conjunctivitis, chalazion, or significant blepharitis

**PROTOCOL TITLE: Micropulse for suppression of diabetic macular edema  
“PULSE STUDY”**

**7) Study Timelines**

- The duration of an individual subject’s participation in the study will be two years which will include at least 10 total visits at various time points including on the day of enrollment, followed by 1, 3, 6, 9, and 12, 15, 18, 21, 24 months after the day of enrollment
- The duration anticipated to enroll all study subjects is 1 year
- The estimated date for the investigators to complete this study is December 2023
- 36 eyes will be enrolled based on power calculations for 80% power assuming at least 40% of eyes monitored by observation alone will experience vision loss to 20/40 or worse, and that SML treatment will reduce that value to 15%, using a 2:1 ratio for randomization (2 treatment : 1 observation (sham)). The ETDRS study showed that among eyes with good visual acuity (20/25 or better), 40% will experience a visual acuity decrease by 5 letters or more. We assume a higher rate among eyes with 20/32 or better.

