## **PROTOCOL TITLE: Micropulse for suppression of diabetic macular edema “PULSE STUDY”**

### **9) Procedures Involved**

This is a randomized, controlled clinical trial comparing subthreshold micropulse laser versus sham laser treatment for eyes with diabetic macular edema with good visual acuity of 20/32 or better. After signing written consent and enrolling in the study, patients will be randomized to receive either subthreshold micropulse laser treatment or no treatment (sham). Randomization will occur as a ratio of 2:1 and will take place during the clinic visit. A block randomization scheme will be created before the study begins to ensure appropriate treatment allocation among the two groups. At the time of randomization, only one eye will be randomized to either the treatment or observation. If both eyes meet the inclusion criteria, one eye (worse eye) will be assigned to the treatment group and the fellow eye to the sham treatment group. Subjects selected for the study will then undergo a complete ophthalmic examination, including measurements of best corrected visual acuity, low luminance visual acuity, contrast sensitivity (using ETDRS testing with a masked coordinator), intraocular pressure, slit lamp exam including documentation of lens status, and dilated funduscopy exam with standard dilating agents used at the UC Davis Eye Center. Subjects will then undergo baseline imaging with SD-OCT and fundus autofluorescence (FAF) using the Spectralis OCT+SLO instrument (Heidelberg Engineering, Heidelberg, Germany) and Optos (Optos Inc.). The Optos imaging system will only be used as a back up to the Heidelberg, as well as microperimetry testing using Nidek MP-1 instrument (Padova, Italy). Both the use of OCT, FAF, and microperimetry testing are within the standard of care for the management of DME.

For OCT and FAF, a lubricating artificial tear drop may be used on subjects with dry eyes to enhance image quality as is routinely done. Each eye will have 3-4 images acquired, which will take approximately 30-45 seconds for each eye. OCT imaging must include at least one high resolution scan across the fovea, and central macular thickness measured as determined using the OCT instrument's algorithm. FAF imaging must include the entire macular region through which the micropulse laser treatment will be applied.

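### The 80% power claimed for 36 eyes does not follow from the protocol's own rates and 2:1 ratio; power is about 39% at two-sided 5% and 51% at one-sided 5%

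*Protocol*

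**What the plan says.** The only sample-size justification is in Protocol section 7 (Study Timelines): "36 eyes will be enrolled based on power calculations for 80% power assuming at least 40% of eyes monitored by observation alone" go on to lose vision to 20/40 or worse, and that "SML treatment will reduce that value to 15%, using a 2:1 ratio for randomization". The total, the power, both event rates and the allocation ratio are therefore all given. The significance level, its sidedness and the test are not.

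The 40% is supported by a result from the ETDRS study in eyes at 20/25 or better, of which "40% will experience a visual acuity decrease by 5 letters or more". The section ends: "We assume a higher rate among eyes with 20/32 or better". No figure for the higher rate follows.

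Three other places bear on the calculation:

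- Section 8 gives the first primary outcome as "Proportion of patients with vision loss to 20/40 or worse on ETDRS testing on two visits" no more than 28 days apart, so the event must be confirmed.
- Section 6 admits eyes with "Best corrected visual acuity of 20/32 or better on ETDRS testing".
- Section 9 says that when both eyes qualify, "one eye (worse eye) will be assigned to the treatment group and the fellow eye to the sham treatment group".

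**The concern.** A difference of 25 percentage points between arms of 24 and 12 eyes is hard to detect, and 80% power looked far too high for it. If the claim is wrong, the trial's size has no valid basis in the document. Should SML work exactly as assumed, a 36-eye trial tested at two-sided 5% would more likely than not miss significance. Readers told that it had 80% power could then take the result as evidence that SML does not work.

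**Working it through.** **Inputs from Protocol section 7:** 36 eyes in total; 2:1, hence 24 SML and 12 sham; event rates 15% (SML) and 40% (sham); claimed power 80%.

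**Assumed, because not stated:** two-sided 5%, with one-sided 5% as the lenient alternative; independent eyes; no dropout (any dropout lowers power).

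**1. Trying to reproduce 80%** (two proportions, normal approximation, pooled variance under the null)

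- Pooled rate = (24 × 0.15 + 12 × 0.40) / 36 = 8.4 / 36 = 0.2333
- SE under the null = √[0.2333 × 0.7667 × (1/24 + 1/12)] = 0.1495
- SE under the alternative = √[0.15 × 0.85/24 + 0.40 × 0.60/12] = 0.1591
- Power, two-sided 5% = Φ[(0.25 − 1.96 × 0.1495) / 0.1591] = Φ(−0.27) = **0.393**
- Power, one-sided 5% (1.645 in place of 1.96) = **0.510**

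Other methods at 24/12:

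| Method | Two-sided 5% | One-sided 5% |
|---|---|---|
| Pooled normal | 39.3% | 51.0% |
| Unpooled normal | 34.9% | 47.1% |
| Arcsine | 36.8% | 49.2% |
| Chi-square, exact enumeration | 41.9% | 49.9% |
| Fisher's exact | 30.5% | 35.8% |

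Relaxing the level further, the pooled formula gives 64% at one-sided 10% and 78% at one-sided 20%. It reaches 80% at a one-sided level of about 22%. The stated figure is not reproduced.

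**2. Size that would give 80% at 2:1**

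- Two-sided 5%: 36 sham + 72 SML = 108 eyes, power 81.0%. With 35 + 70 = 105 eyes it is 79.99%, just short.
- One-sided 5%: 28 + 56 = 84 eyes, power 80.4%.

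The smaller arm at two-sided 5% is 36, the same number as the stated total. An arm size may have been recorded as the total. That is an inference; it holds only at two-sided 5% and by a narrow rounding margin, and the finding does not depend on it.

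**3. A sham rate above 40%** (SML at 15%, 24/12, two-sided 5%)

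| Sham rate | Pooled normal | Fisher's exact |
|---|---|---|
| 30% | 20% | 14% |
| 40% | 39% | 31% |
| 50% | 61% | 51% |
| 55% | 71% | 61% |
| 60% | 80% | 71% |
| 65% | 87% | 80% |

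By the normal approximation, 80% is reached at a sham rate of 60.2%. At one-sided 5%, a rate of 55% gives 80.4%.

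**4. Fellow eyes**

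Take the extreme case of 18 patients, all contributing one eye to each arm. With within-patient correlation ρ (assumed), the probability that both eyes have the event is 0.06 + ρ√(0.15 × 0.85 × 0.40 × 0.60). This cannot exceed 0.15, so ρ is at most 0.514. Power at two-sided 5%:

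| ρ | Wald | McNemar approximation | Exact McNemar |
|---|---|---|---|
| 0 | 42% | 36% | 23% |
| 0.3 | 54% | 46% | 27% |
| 0.5 | 68% | 56% | 28% |

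At ρ = 0.514 the Wald figure is 69%. At one-sided 5% it is 78% for ρ = 0.5 and 79% for ρ = 0.514. An 18:18 split of independent eyes gives 38.5% at two-sided 5%.

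**5. Precision**

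The 95% confidence interval for the risk difference at 24/12 has half-width 1.96 × 0.1591 = 0.312, about ±31 points, which is wider than the 25-point effect sought.

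**The case against.** The best defence is that section 7 describes 40% as a minimum and says a higher rate is expected, so the calculation may have used a larger sham rate. But a minimum is the value at which the claimed power should still hold, and no other value is given. The rate needed is about 60%, or 55% at one-sided 5%. If such a rate was used, the remedy is to state it, and the fix allows for that.

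A second defence is pairing. At one-sided 5% the all-bilateral case comes close, at 79%, and at one-sided 10% it passes 80% (87% by Wald at ρ = 0.5). Those cases need every patient to be bilateral and near-maximal correlation, and they abandon the 2:1 ratio on which the stated calculation rests. The claim that pairing does not rescue 80% is therefore limited to 5% levels.

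A third is that the level and test may be left to the SAP. That is fair, and their absence is not the finding. The range is shown because they are absent, and neither 5% level recovers 80%.

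On the 40% itself, the objection partly stands. The protocol presents the rate as an assumption, and a loss of five letters *or more* from 20/25 can reach 20/40. Taking five letters as one chart line (a conversion the protocol does not give), a loss of just five letters reaches 20/40 only from 20/32; from 20/25 it ends at 20/32. The ETDRS figure is also described without the confirmation at a second visit that section 8 requires. It therefore supports the 40% only indirectly. This is a secondary point.

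**Conclusion.** The concern holds. On the protocol's own rates and ratio, 36 eyes give about 39% power at two-sided 5% (31% to 42% across the methods tried) and about 51% at one-sided 5% (36% to 51%), not 80%. The total needed for 80% is about 108 eyes at two-sided 5%, or 84 at one-sided 5%. The 24/12 figures assume independent eyes and no dropout. The significance level is an assumption, but the conclusion is the same at either 5% level. As the claim is the sole basis for the trial's size, it must be corrected.

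**What to change.** In Protocol section 7, replace the 80% claim and state the significance level and test. If two-sided 5% is the level chosen, wording could be:

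> With 36 independent eyes (24 SML, 12 sham), power to detect 40% versus 15% at two-sided 5% is about 39% (31% by Fisher's exact test). At 2:1, 80% power would need about 108 eyes (72 + 36). The 95% confidence interval for the risk difference is about ±31 percentage points. The 40% rate of confirmed loss to 20/40 or worse is an assumption. With SML at 15%, power is about 20%, 39%, 61% and 80% at sham rates of 30%, 40%, 50% and 60%.

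Add that patients contributing both eyes move the split toward 1:1 and make those eyes paired, so the figures apply to independent eyes.

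If a sham rate above 40% was in fact used, give that rate, its justification and the level and test that yield 80%.

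The cost is protocol wording only, and no extra eyes are required. The drawback is a less favourable power statement. Whether to enlarge the trial, or to present it as estimation or a pilot, is the sponsor's choice.

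### The 40% sham event rate behind the sample size is not supported by the figure cited for it, which describes a different event; the true rate could lie below or above 40%

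*Protocol*

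**What the plan says.** The sample-size bullet in section 7 (Study Timelines) states that "36 eyes will be enrolled based on power calculations for 80% power". Its inputs are a sham rate, worded as "assuming at least 40% of eyes monitored by observation alone will experience vision loss to 20/40 or worse", an SML rate of 15%, and 2:1 allocation. The support offered comes next: "40% will experience a visual acuity decrease by 5 letters or more", which is an ETDRS result for eyes at 20/25 or better. The bullet closes with "We assume a higher rate among eyes with 20/32 or better".

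The first primary outcome in section 8 (Study Endpoints) is "Proportion of patients with vision loss to 20/40 or worse on ETDRS testing on two visits" no more than 28 days apart, read at 12 and 24 months. Section 9 (Procedures Involved) makes the repeat visit a condition of reaching the endpoint. Section 8 also lists loss of 5 letters or more, but as a separate secondary outcome. Section 6 admits eyes at 20/32 or better.

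**The concern.** The same number, 40%, is attached first to loss to 20/40 and then to loss of 5 letters or more, as if the second established the first. The Protocol's own endpoint list treats them as two outcomes. The closing sentence on eyes at 20/32 or better deals with the population only. It gives no figure and no source, and it does not touch the 20/40 threshold, the confirmation visit or the time point.

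This is the document's only sample-size justification, and the number of events depends directly on the rate. If the rate is wrong, readers will weigh a null result against a power claim that the cited evidence cannot carry.

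**Working it through.** **Step 1. The two events side by side.**

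| | Figure cited for the 40% | Trial endpoint |
|---|---|---|
| Event | loss of 5 letters or more | acuity of 20/40 or worse |
| Type | relative to baseline | absolute threshold |
| Eyes | 20/25 or better | 20/32 or better |
| Confirmation | none mentioned | repeat visit within 28 days |
| Time point | none given | 12 and 24 months |

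**Step 2. Direction.** Assume 5 letters per ETDRS line, with 20/25, 20/32 and 20/40 as successive lines.
- Eye at 20/25: a 5-letter loss leads to 20/32, so reaching 20/40 takes about two lines. Eyes with better acuity need more. Every such eye that reaches 20/40 has also lost at least 5 letters, so over the same follow-up 40% is an upper bound in this group. Confirmation can only lower the rate.
- Eye at 20/32: about one line or less leads to 20/40. Here the endpoint can be as easy to reach as a 5-letter loss, or easier, before confirmation is applied.

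The overall sham rate is (1 − w) × a + w × b, where w is the share of eyes at 20/32, a is the rate at 20/25 or better (at most 40%) and b is the rate at 20/32. The Protocol gives none of w, a or b, so the total may fall on either side of 40%.

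**Step 3. The plan's own figure.** Inputs from section 7: sham 0.40, SML 0.15, 2:1, 80% power. Alpha is not stated; two-sided 5% is assumed. With pooled rate p = (0.40 + 2 × 0.15)/3 = 0.2333,

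n(sham) = [1.960 × √(1.5 × 0.2333 × 0.7667) + 0.842 × √(0.40 × 0.60 + 0.15 × 0.85/2)]² / 0.25² = (1.015 + 0.464)² / 0.0625 ≈ 35.0.

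The total is 3 × 35.0 ≈ 105 eyes, or 36 + 72 = 108 when the sham arm is rounded up. The stated 36 is not reproduced. One-sided 5% still needs 84.

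**Step 4. Power of 36 eyes across sham rates.** All tables for 24 SML and 12 sham eyes were enumerated with exact binomial probabilities, counting those with two-sided p ≤ 0.05. The SML rate is 0.15/0.40 = 0.375 times the sham rate, which is the planned 62.5% reduction. Expected events are 12 × sham rate + 24 × SML rate. The 20–60% range is assumed, because the document gives no rate for confirmed loss to 20/40.

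| Sham | SML | Expected events | Power, Fisher | Power, uncorrected chi-square | Eyes for 80% (unrounded–rounded up) |
|---|---|---|---|---|---|
| 20% | 7.5% | 4.2 | 15% | 21% | 250–252 |
| 30% | 11.25% | 6.3 | 24% | 30% | 153–156 |
| 40% | 15% | 8.4 | 30% | 42% | 105–108 |
| 50% | 18.75% | 10.5 | 38% | 54% | 76–78 |
| 60% | 22.5% | 12.6 | 48% | 64% | 56–57 |

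If SML is held at 15% instead, a sham rate of 60% gives 71% (Fisher) or 83% (chi-square).

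**The case against.** The Protocol labels the 40% as an assumption, words it as a minimum, and expects a higher rate once eyes at 20/32 are included. Using an imperfect proxy where no rate exists for the exact endpoint is common practice. This stands in part: the 40% may be used as a declared assumption, and it would be too strong to say that it has no basis. What fails is the narrower step of offering the 5-letter figure as support for it.

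A reader might also infer that 40% is too high because the trial endpoint is the harder event, so that the mismatch must worsen the power. The documents do not support that. The argument holds only for eyes at 20/25 or better. The trial also admits eyes at 20/32, and no baseline mix is given. For the same reason a power range that stops at 40% would leave out the sponsor's own higher-rate scenario.

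A third tempting reading is that the mismatch explains the gap between 80% and the power of 36 eyes. It does not. With 40% versus 15% fully granted, power is already only 30% (Fisher) or 42% (chi-square). That gap is an arithmetic error in the 36-eye figure and is a separate matter. The rate question accounts only for movement up or down from the 40% row.

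**Conclusion.** The point holds as a gap in justification whose direction is unknown. The cited figure does not support a 40% rate of confirmed loss to 20/40, and nothing else in the Protocol does.

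The rate matters. At the planned relative reduction, moving the sham rate from 20% to 60% takes the power of 36 eyes from 15% to 48% (Fisher) or from 21% to 64% (chi-square), and no rate in that range reaches 80%. The one calculated case that does is the chi-square test with sham at 60% and SML held at 15%; Fisher's test gives 71% there.

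These results assume a two-sided 5% level, a 24/12 split and independent eyes without dropout. The statement about direction also assumes 5-letter lines.

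**What to change.** In the sample-size bullet of section 7:

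1. Remove the implication that the ETDRS 5-letter result supports a 40% rate of loss to 20/40. It may stay as background if it is described as a different outcome in a narrower group.
2. State the assumed sham rate of confirmed loss to 20/40 or worse by a named month, and label it as an assumption.
3. Replace the 80% claim with the power of 36 eyes (24 SML, 12 sham) over sham rates on both sides of 40%, for example 20–60%. Name the test and alpha, and say whether the relative reduction or the 15% SML rate is held fixed.

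The same rewrite can correct the separate arithmetic error, since 40% versus 15% needs about 105–108 eyes. Giving separate rates for eyes at 20/32 and at 20/25 or better would make the assumption clearer but is optional.

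The cost is a few sentences, a short recalculation and a less favourable stated power. No extra patients are needed and study procedures do not change.
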